4.3 Justification for Dose

Dysport 40 U has already been shown to be well tolerated when injected into the EDB [[Pons 2019](#)], as well as demonstrating an absence of local diffusion to the adjacent muscles. This dose level was also associated to a remaining CMAP inhibition 6 months post-injection.

When applying a ratio of 2.5 (Dysport) for 1 (Botox/Xeomin), which is based on the maximum recommended total doses in the USPI from the FDA from adult upper limb spasticity and glabellar lines indications, a dose of 16 U is selected for Botox and Xeomin. Doses of 16 U Botox or Xeomin were also shown to be safe when injected into the EDB [[Wohlfarth 2007](#)].

4.4 End of Study Definition

The end of the study (EoS) is defined as the date of the last visit of the last participant in the study or last scheduled procedure shown in the SoA for the last participant.

A participant is considered to have completed the study if he has completed all phases of the study including the last visit or the last scheduled procedure shown in the SoA.

5 STUDY POPULATION

Prospective approval of protocol deviations to recruitment and enrolment criteria, also known as protocol waivers or exemptions, is not permitted.

5.1 Inclusion Criteria

Participants are eligible to be included in the study only if all the following criteria apply:

Age

1. Participant must be between 18 to 65 years of age inclusive, at the time of signing the informed consent.

Type of Participant and Disease Characteristics

2. Participants who are overtly healthy as determined by medical evaluation including medical history, physical examination, laboratory tests, vital signs and cardiac monitoring.

Weight

3. A body mass index (BMI) within the range 18 and 30 kg/m² (inclusive).

Sex

4. Participants are male.

Informed Consent

5. Capable of giving signed informed consent as described in Appendix 10.1 which includes compliance with the requirements and restrictions listed in the informed consent form (ICF) and in this protocol.

5.2 Exclusion Criteria

Participants are excluded from the study if any of the following criteria apply:

Medical Conditions

1. Any medical condition that may put the participant at risk with exposure to BoNT, including diagnosed myasthenia gravis, Eaton-Lambert syndrome, amyotrophic lateral sclerosis, or any other disease that might interfere with neuromuscular function.
2. Complication or history of peripheral neuropathy (e.g. as a result of diabetes mellitus), nerve root impairment or muscle disease.
3. Has or has a history of breathing problems, such as asthma or emphysema.
4. Has or has a history of swallowing problems.
5. Has or has a history of bleeding problems.
6. Has or has a history of blurred or double vision.
7. Has or has a history of dysarthria or dysphonia.

Prior/concomitant Therapy

8. Previous treatment with BoNT (any serotype) during the past 6 months.
9. Has received a COVID-19 vaccine injection within 7 days before the planned study intervention injection or is planning/likely to be vaccinated within 7 days after the planned study intervention injection.
10. Use of agents that could interfere with neuromuscular transmission, including calcium channel blockers, penicillamine, aminoglycosides, lincosamides, polymixins, magnesium sulphate, anticholinesterases, succinylcholine and quinidine.
11. Use of concomitant therapy which, in the investigator's opinion, would interfere with the evaluation of the safety or efficacy of the study intervention, including medications

affecting bleeding disorders (e.g. antiplatelet agents and/or anticoagulants given for treatment or prevention of cardiovascular/cerebrovascular diseases).

12. Any planned surgery of the foot.

Prior/concurrent Clinical Study Experience

13. Use of any experimental device within 3 months or use of any treatment with an experimental drug within five times the documented terminal half-life of the respective drug or its metabolites or if the half-life is unknown within 3 months prior to the start of the study (prior to Baseline) and during the conduct of the study.
14. Participation in a concurrent study of another investigational drug or device.

Diagnostic Assessments

15. Known positive for hepatitis B antigen, or hepatitis C virus antibody, or for human immunodeficiency virus (HIV) or a diagnosis of acquired immunodeficiency syndrome.
16. Clinically diagnosed significant anxiety disorder, or any other significant psychiatric disorder (e.g. depression) that might interfere with the participant's participation in the study.

Other Exclusions

17. Known hypersensitivity to any of the components of the Dysport/ Botox/ Xeomin formulation (which includes human serum albumin, lactose, sucrose) or allergy to cow's milk protein.
18. Has recent evidence of alcohol abuse, positive drugs of abuse screen, or other relevant neuropsychiatric condition in the opinion of the investigator.
19. Has any mental condition rendering the participant unable to understand the nature, scope and possible consequences of the study.
20. Is likely to be noncompliant or uncooperative during the study, in the judgment of the investigator.
21. Resides in an institution by administrative or court order
22. Is a sponsor employee or clinical research unit personnel directly affiliated with this study or is an immediate family member. Immediate family is defined as a spouse, parent, child or sibling whether biological or legally adopted.
23. Any uncontrolled systemic disease or other significant medical condition which would be harmful for the participant to be entered into the study or continue participation are considered as exclusion criteria.

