4.2 Scientific Rationale for Study Design

The higher quantity of neurotoxin in Dysport than Botox or Xeomin at the approved FDA dose used in therapeutic and aesthetic indications may contribute to the prolonged duration of action exhibited by Dysport compared with other BoNT-A products [[Field 2018](#)]. Using the same dose ratio, this study aims to demonstrate a longer duration of action of Dysport compared to Botox and Xeomin in a well-known and recognized pharmacodynamic model in healthy male participants.

This model uses the EDB muscle and records its compound muscle action potential (CMAP) following supramaximal stimulation of the corresponding nerve. The present design will capture the CMAP of injected EDB with either Dysport, Botox or Xeomin. The expected inhibition of the electrophysiological signal following BoNT administration will be followed in parallel study intervention groups and blinded conditions, up to 40 weeks after injection aiming at capturing recovery of the inhibition.

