9.2 Sample Size Determination

Approximately 48 participants will be screened to achieve 15 participants randomised to Dysport, 15 participants randomised to Botox and 15 participants randomised to Xeomin using a 1:1:1 randomisation ratio and assuming a screening failure rate of 5%.

The sample size calculation is based on the primary efficacy estimand and its endpoint relative change from baseline in EDB CMAP total amplitude at Week 28. Using a 2-sided t-test at the 5% significance level, the chosen sample size provides at least 88% power to detect a treatment difference of 18% relative change from baseline in the Dysport arm than in a comparator arm assuming a common standard deviation in all treatment arms of 15% as observed for Dysport in a historical study CCI – Part B. The treatment difference is based on the observed average EDB CMAP total amplitude at 6 months of Dysport 40 U (CCI – Part B) and of Botox and Xeomin 16 U in Wohlfarth [Wohlfarth 2007]. The power analysis was conducted with NQuery version 8.4.1.0. Given the made assumptions and the sample size of 15 participants per arm the probability to show superiority of Dysport to both comparators

simultaneously is at least 81%, as shown in a simulation study conducted with software R version 4.0.3.

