9.4.1.1 Pharmacodynamic Evaluation

Individual pharmacodynamic endpoints will be tabulated by treatment and timepoint. For the EDB CMAP, three measurements of CMAP will be taken at each timepoint including baseline. The mean of these three measurements will be used to determine the parameter relative change from baseline in CMAP total amplitude, used in primary and secondary analyses of the EDB CMAP related endpoints. The baseline value used for the analyses will be the average of six measurements, the three measurements at screening and the three measurements at baseline.

At each visit time to latency will be evaluated. Skin temperature and stimulation intensity will be also collected for quality control and descriptive statistics.

Individual pharmacodynamic endpoints will be tabulated by treatment allocation and timepoint. Further details on general statistical considerations will be specified in the statistical analysis plan (SAP).

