9.4.3 Analysis of Secondary Endpoints

9.4.3.1 Incidence of Recovery of CMAP Total Amplitude at Week 28 and Week 40

Recovery of CMAP total amplitude is defined as a return of total amplitude to at least 85% of the Baseline value. Incidence of recovery of CMAP total amplitude at Weeks 28 and 40 will be analysed for each of the two timepoints by estimating proportion of participants with recovery in each of the treatment arms, p_D in the Dysport arm, p_B in the Botox arm, p_X in the Xeomin arm, as well as the risk differences $p_D - p_B$ and $p_D - p_X$ with point estimates as well as according exact (Clopper-Pearson) 95% confidence intervals for p_D , p_B and p_X and exact unconditional 95% confidence interval for the risk differences.

A Fisher’s Exact Test (one-sided, significance level 2.5%) will be used for testing each of the comparisons of Dysport to Botox or Xeomin respectively in the framework of the multiple testing procedure described in Section 9.1.

9.4.3.2 CMAP Total Amplitude at Week 40

CMAP total amplitude at Week 40 will be analysed using the same MMRM model used for the primary analysis.

9.4.3.3 *Time to Onset of Action*

Time to onset of action will be analysed descriptively. Onset of action is defined as the first timepoint where EDB CMAP total amplitude is 85% or lower than the Baseline value.

9.4.3.4 *Duration of Response*

Duration of response will be analysed descriptively. Duration of response is defined as the time between onset of action and recovery of CMAP total amplitude (where recovery is defined as return to at least 85% of the Baseline value).

9.4.3.5 *Maximal Effect*

Maximal Effect for each participant is defined as the maximal measured inhibition of CMAP amplitude of stimulated EDB. Maximal Effect will be analysed descriptively.

9.4.3.6 *Time to Maximal Effect*

Time to maximal effect will be analysed descriptively. Time to maximal effect is defined on an individual basis as the time between Baseline and the timepoint of maximal inhibition of CMAP amplitude of stimulated EDB.

9.4.4 *Safety Analyses*

All safety analyses will be made on the Safety Population.

Summary statistics will be presented by study intervention group and overall for vital signs, physical examination, at each assessment.

Adverse Events

All AEs will be coded according to the Medical Dictionary for Regulatory Activities (MedDRA) (last applicable version) and will be classified by MedDRA preferred term and system organ class.

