5.7.2 Analysis of Primary Pharmacodynamic Endpoint

5.7.2.1 Endpoint, Treatment Effect and Estimand Definition

To assess the primary objective, the primary estimand has the following key attributes:

- Population of interest: healthy adult male participants as defined by the listed inclusion/exclusion criteria in Section 5.1 and 5.2 of the protocol.
- Variable/endpoint of interest: CMAP total amplitude at Week 28, measured as percentage relative to baseline (%), calculated as [value at Week 28 (mean of the three measurements/baseline value (means of the six measurements)]*100.

- ICEs are the following:
 - a) Study discontinuation
 - b1) PDs with potential impact on relevant CMAP total amplitude assessments (i.e. participant received the wrong study intervention and CMAP at Week 28 performed out of a specified time window ($> +/- 2$ weeks))
 - b2) PDs with no expected impact on relevant CMAP assessments (e.g. other time window violations, PDs related to covid-19)
- Treatment regimen: Dysport, Botox or Xeomin will be administered as described in Section 6 of the protocol and potential intake of permitted concomitant medications (for a list see Section 6.8 of the protocol).
- Population-level summary of the treatment effect of interest: the difference in average percentage relative to baseline in each study intervention group in CMAP total amplitude at the respective timepoint.

For ICEs (a) and (b1) a hypothetical strategy will be used, the treatment difference which would have been measured if the ICE would not have happened is of interest and will be assessed taking into account the long term pharmacodynamic effect of the investigated compounds. This implies that assessments after the occurrence of a major protocol deviation interfering with CMAP total amplitude will be ignored for the primary analysis. No imputation of missing CMAP will be done (MMRM analysis, please refer to [section 5.7.1.2](#)). For ICEs (b2), a treatment policy will be used.

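### The 6-month BoNT exclusion does not rule out a depressed EDB baseline after an earlier injection into the study muscle: probably rare, but cheap to close

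*Protocol*

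**What the plan says.** Exclusion 8 (Protocol 5.2) is the only criterion that names earlier toxin: "Previous treatment with BoNT (any serotype) during the past 6 months". It draws no distinction by muscle, so an EDB injection is treated like one anywhere else.

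On how long the effect lasts in this muscle, the dose justification (Protocol 4.3) says of Dysport 40 U: "This dose level was also associated to a remaining CMAP inhibition 6 months post-injection". The design rationale (Protocol 4.2) has the signal followed "up to 40 weeks after injection aiming at capturing recovery of the inhibition".

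On the use of baseline, Protocol 9.4.1.1 states: "The baseline value used for the analyses will be the average of six measurements". Three of these come from screening and three from Day 1, at most 14 days apart. SAP 5.7.2.1 defines the primary variable as a percentage of that baseline, "calculated as [value at Week 28 (mean of the three measurements/baseline value (means of the six measurements)]*100". Recovery uses the same reference (Protocol 9.4.3.1): "Recovery of CMAP total amplitude is defined as a return of total amplitude to at least 85% of the Baseline value". Onset is the first visit at or below 85% of baseline (SAP 5.7.4).

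**The concern.** When it measures the effect, the protocol treats 6 months as too early for the EDB to have recovered. When it screens, it treats 6 months as long enough. For toxin given elsewhere this hardly matters. For a man injected earlier in the EDB now to be studied, the screening and Day 1 recordings could be taken on a muscle that is still partly blocked.

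If that old block wears off during follow-up, his later amplitudes are divided by a denominator that is too small. His Week 28 and Week 40 percentages are then too high, he may cross the recovery threshold too soon, and he may reach onset late. SAP 5.7.3.1 counts recovery as reached at every visit after the first crossing, so a spurious recovery would persist. With 15 men per arm, one distorted value carries some weight.

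**Working it through.** **1. The plan's own figure, for scale.** Inputs from Protocol 9.2: 15 per arm, difference 18, SD 15, two-sided 5% t-test. The noncentrality is 18 / (15 × √(2/15)) = 3.29 on 28 degrees of freedom, which gives power of 88.7%. The plan's claim reads: "Using a 2-sided t-test at the 5% significance level, the chosen sample size provides at least 88% power". Simulating three normal arms with a shared Dysport arm gives 81.4% for success against both comparators, where the plan states at least 81%. Both figures reproduce, and the sample size is not in question.

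**2. The intervals side by side.** The exclusion covers 6 months, about 26 weeks. Inhibition is reported as still present at 6 months, the primary endpoint is at Week 28, and follow-up for recovery runs to Week 40. The exclusion interval is therefore no longer than the persistence the protocol reports.

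**3. Is the gap closed elsewhere?**
- Other exclusions: 2 concerns neuropathy, nerve root and muscle disease. 10 lists interfering agents without naming BoNT. 13 concerns experimental products, for five half-lives or 3 months.
- No minimum baseline CMAP, left-right comparison or baseline stability is required.
- The PD set (Protocol 9.3) needs only the appropriate dose, a baseline and one later CMAP.
- SAP 5.5 lists prior BoNT therapies, but no analysis uses the listing. SAP 5.7.2.3 plans no sensitivity analysis.
- Baseline CMAP is a model covariate, but it cannot tell a naturally small amplitude from a temporarily suppressed one.

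None of these removes or corrects such a participant.

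**4. Size for one participant.** Assumptions, none from the documents: baseline is depressed by a fraction x, the old block has cleared by Week 28, and the true Week 28 value is 60% of the unimpaired baseline. The recorded value is 60 / (1 − x).

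| x | 1/(1 − x) | 60% is recorded as | Shift (points) | Shift in a 15-person arm mean |
|---|---|---|---|---|
| 15% | 1.176 | 70.6% | 10.6 | 10.6/15 = 0.7 |
| 30% | 1.429 | 85.7% | 25.7 | 25.7/15 = 1.7 |

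At x = 30% a man counts as recovered once his true value reaches 0.85 × 0.70 = 59.5%. The 60% example only just crosses.

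For a comparator participant at 78% (60 + 18) the shifts are 13.8 and 33.4 points, or 0.9 and 2.2 in the arm mean.

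**5. Effect on one pairwise comparison.** True means 60 and 78, SD 15, simulated t-tests. The planned analysis is an MMRM, so this gives scale only.

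| Affected participants | x = 15% | x = 30% |
|---|---|---|
| None | 88.7% | 88.7% |
| One, in the Dysport arm | about 85% | 77 to 78% |
| One, in the comparator arm | about 91% | about 92% |
| One in each of the two arms | about 88% | about 83% |

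A single affected man is equally likely to fall in any of the three arms, and in the third he leaves this comparison untouched. The average is about (85 + 91 + 88.7)/3 = 88% for x = 15% and (78 + 92 + 88.7)/3 = 86% for x = 30%.

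With one man in each arm, the 18-point difference is stretched slightly: by (13.8 − 10.6)/15 = 0.2 or (33.4 − 25.7)/15 = 0.5 points. Where the products do not differ, no difference is created on average.

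**The case against.** The strongest reply is that the affected man is hypothetical. The uses listed in Protocol 2 are therapeutic and facial, and the EDB appears there only as a research model. He would have to be a former volunteer in an EDB study, injected in the same foot more than 6 months ago and still inhibited. Nothing in the documents says that the centre has run such studies or would recruit from them. Exclusion 8 is a general washout, while section 4.3 describes one dose in one muscle; the two pull apart only for this man. There are also informal safeguards: CMAP is recorded twice before dosing, and Protocol 8.1.1 locates the point of maximum response in both EDB muscles at screening, so a neurophysiologist might notice a weak or asymmetric muscle.

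Most of this stands. It fixes the priority as low and limits the point to earlier injection into the study muscle. It does not close the gap, because no rule tells anyone to act on a low or asymmetric reading.

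Three stronger readings are tempting, and the documents do not support them:
- That any earlier BoNT, at any site, compromises baseline. Sections 2.2 and 4.3 report no local diffusion to adjacent muscles at 40 U, and nothing suggests that toxin given elsewhere lowers EDB CMAP.
- That power falls to 77 or 78%. This needs the affected man to land in the Dysport arm; in a comparator arm he raises power.
- That the exclusion should be at least 40 weeks. Forty weeks is the length of follow-up, not a documented clearance time.

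**Conclusion.** The point holds in limited form. For earlier injection into the study EDB, exclusion 8 does not fit the protocol's own statement that inhibition remains at 6 months, and nothing else protects the denominator of the primary endpoint or the 85% thresholds.

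The consequence is noise or chance imbalance. Randomisation means that it does not favour one product. Under the assumptions in the working, one affected participant moves his arm mean by about 0.7 to 1.7 points and changes average power for a comparison from 88.7% to about 86 to 88%. The range rests on an assumed depression of 15 to 30%, clearance by Week 28 and a true value of 60%. If the old block clears only partly, the shift is smaller. The documents give neither the frequency of earlier EDB injection nor the residual inhibition, so this is an illustration and not an estimate. It is an inexpensive improvement, not a threat to the trial's conclusion.

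**What to change.** Reconcile exclusion 8 with Protocol 4.2 and 4.3 for earlier injection into the study muscle. One way is to use only a foot whose EDB has had no earlier BoNT injection. If the sponsor prefers an interval, it should be chosen and justified by the sponsor from data on recovery in this muscle; the documents supply no such figure.

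The cost is one eligibility line in an amendment and perhaps a few healthy volunteers who become ineligible. If enrolment has already closed, the listing of prior BoNT therapies in SAP 5.5 is the place to look for any such participant before unblinding.

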5.3 Lifestyle Considerations

Besides restrictions already presented in the exclusion criteria (see Section 5.2), participants will be requested to abstain from alcohol for 24 hours prior to admission to the clinical research unit. Excessive alcohol consumption (>14 units per week) should be avoided for the duration of the study. Participants are also requested to abstain from recreational drugs abuse from 48 hours prior to Day -1 and until discharge from the study. Participants will be requested to refrain from smoking while they are in the unit and should also refrain from vigorous physical activity from Screening until the completion of the study.

5.4 Screen Failures

Screen failures are defined as participants who consent to participate in the clinical study but are not subsequently randomly assigned to study intervention/entered in the study. A minimal set of screen failure information is required to ensure transparent reporting of screen failure

participants to meet the Consolidated Standards of Reporting Trials (CONSORT) publishing requirements and to respond to queries from regulatory authorities. Minimal information includes demography, reason for screen failure, eligibility criteria and any serious adverse event (SAE).

Individuals who do not meet the criteria for participation in this study (screen failure) may be rescreened once.

Rescreened participants will have to re-sign an (new) ICF and a new participant number will be allocated. All screening assessments need to be repeated for the rescreened participant.

5.5 Criteria for Temporarily Delaying Enrolment/Randomisation/Administration of Study Intervention Administration

In case of suspected or confirmed COVID-19 (SARS-CoV-2) infection at the Baseline visit (Day 1), the study intervention administration may be temporarily postponed depending on the participant's clinical presentation. See Section [7.1.1](#) for further details.

6 STUDY INTERVENTION AND CONCOMITANT THERAPY

Study intervention is defined as any investigational intervention(s), marketed product(s), placebo, or medical device(s) intended to be administered to a study participant according to the study protocol.

